5.4.4. Rash/Hypersensitivity Stopping Criteria

A subject presenting with a Grade 3 AE or higher rash (diffuse macular, maculopapular, OR morbilliform rash with vesicles or limited number of bullae; OR superficial ulcerations of mucous membrane limited to 1 site) or a Grade 2 rash (diffuse macular, maculopapular, or morbilliform rash; OR target lesions) with evidence of systemic involvement will be followed as appropriate until resolution of the AE(s).

5.5. Subject and Study Completion

A completed subject is one who has completed all phases of the study including the Follow-up visit.

The end of the study is defined as the last subject's last visit.

6. STUDY TREATMENT

6.1. Investigational Product and Other Study Treatment

The term 'study treatment' is used throughout the protocol to describe any combination of products received by the subject as per the protocol design. Study treatment may therefore refer to the individual study treatments or the combination of those study treatments.

	Study Treatment			
Product name:	Gepotidacin (GSK2140944) capsule	Gepotidacin (GSK2140944B) RC tablet	Gepotidacin (GSK2140944B) HSWG tablet	Placebo tablet
Formulation description:	Immediate release capsules containing gepotidacin (mesylate salt) and inactive formulation excipients	Immediate release tablets containing gepotidacin (free base) and inactive formulation excipients	Immediate release tablets containing gepotidacin (free base) and inactive formulation excipients	Immediate release tablets containing only inactive formulation excipients
Dosage form:	Capsule	Tablet	Tablet	Tablet
Unit dose strength/ Dosage level:	500 mg/ 1500 mg (3 × 500 mg)	750 mg/ 1500 mg (2 × 750 mg) 2250 mg (3 × 750 mg) 3000 mg (4 × 750 mg)	750 mg/ 1500 mg (2 × 750 mg)	Not applicable
Route of Administration:	Oral	Oral	Oral	Oral
Dosing instructions:	Dose with 240 mL of water. Up to an additional 100 mL of water may be given to assist in swallowing capsules.	Dose with 240 mL of water. Up to an additional 100 mL of water may be given to assist in swallowing tablets.	Dose with 240 mL of water. Up to an additional 100 mL of water may be given to assist in swallowing tablets.	Dose with 240 mL of water. Up to an additional 100 mL of water may be given to assist in swallowing tablets.
Physical description:	Pink Gelatin size 00 capsule with no identifying markings containing slightly agglomerated pale yellow to grayish yellow to yellowish gray powder.	A capsule-shape white film-coated tablet with no identifying markings.	An oval shape white film-coated tablet with no identifying markings.	A capsule-shape white film-coated tablet with no identifying markings.
Manufacturer/ Source of procurement:	GlaxoSmithKline	GlaxoSmithKline	GlaxoSmithKline	GlaxoSmithKline

6.2. Treatment Assignment

Subjects in Part 1a will be assigned to a treatment sequence to receive gepotidacin (GSK2140944) capsules, RC tablets, and HSWG tablets in accordance with the randomization schedule generated by PPD before the start of the study, using validated internal software. Based upon PK, safety, and tolerability data obtained from Part 1a, a decision will be made whether to use the free base RC or HSWG tablet formulation for the remainder of the study. Subjects in Part 1b will be assigned to a treatment sequence to receive the selected tablet formulation under fasted and fed conditions. Japanese subjects in Part 2 will receive 2 different doses of the selected tablet formulation. Japanese subjects in Part 3 will be stratified by gender in a 1:1 ratio and randomized (10 active: 2 placebo) to receive the selected tablet formulation in a fixed sequence or placebo under fed conditions.

A description of each regimen for all study parts is provided in the table below:

Part	Treatment Code	Treatment
1a	A	Gepotidacin 1500 mg (3 x 500 mg) capsules
1a	B	Gepotidacin 1500 mg (2 x 750 mg) RC tablets
1a	C	Gepotidacin 1500 mg (2 x 750 mg) HSWG tablets
1b	D	Gepotidacin 1500 mg (2 x 750 mg) RC or HSWG tablets – fasted
1b	E	Gepotidacin 1500 mg (2 x 750 mg) RC or HSWG tablets – fed
2	B or C	Gepotidacin 1500 mg (2 x 750 mg) RC or HSWG tablets, respectively
2	F	Gepotidacin 3000 mg (4 x 750 mg) RC or HSWG tablets
3	E	Gepotidacin 1500 mg (2 x 750 mg) RC or HSWG tablets – fed
3	G	Gepotidacin 2250 mg (3 x 750 mg) RC or HSWG tablets – fed
3	H	Gepotidacin 3000 mg (4 x 750 mg) RC or HSWG tablets – fed
3	I	Placebo tablets - fed

Subjects will be given a subject number that will be a unique identifier. Once a subject number has been assigned, the number will not be reused even if the subject withdraws from the study before receiving gepotidacin.

6.3. Planned Dose Adjustments

Planned dose adjustments are not allowed during this study.

6.4. Blinding

Parts 1 and 2 will be an open-label study.

Part 3 will be a double-blind (sponsor unblinded) study. The subjects will be completely blinded and the site staff will be blinded to subject-specific treatment assignment. The GSK study team will be unblinded at the aggregate level for decision making throughout the study (e.g. to support dose escalations and use of Bayesian predictive techniques).

Where possible, the GSK/clinical research organization personnel will not have access to subject-specific treatment assignment so as to not potentially introduce bias in discussions with the study site. The pharmacokineticists, statisticians, programmers, and data managers, however, will need access to subject randomization during the course of the study for analysis purposes to support dose adjustments and escalations. Other GSK staff may be included in discussions around dose adjustments and progression if it is deemed necessary and relevant by the above mentioned GSK study team members.

During dosing of a specific cohort, the investigator or treating physician may unblind a subject's treatment assignment only in the case of an emergency, when knowledge of the study treatment is essential for the appropriate clinical management or welfare of the subject. Whenever possible, the investigator must first discuss options with the GSK medical monitor or appropriate GSK study personnel before unblinding the subject's treatment assignment. If this is impractical, the investigator must notify GSK as soon as possible, but without revealing the treatment assignment of the unblinded subject, unless that information is important for the safety of subjects currently in the study. The date and reason for the unblinding must be recorded in the electronic data capture system. In this situation, the subject will be withdrawn from further treatment if the subject's treatment code is unblinded by the investigator or treating physician. The primary reason for discontinuation (the event or condition which led to the unblinding) will be recorded in the electronic data capture system. GSK's Global Clinical Safety and Pharmacovigilance staff may unblind the treatment assignment for any subject with an SAE. If the SAE requires that an expedited regulatory report be sent to 1 or more regulatory agencies, a copy of the report, identifying the subject's treatment assignment, may be sent to the investigator in accordance with local regulations and/or GSK policy.

During the dose escalation safety review, the GSK clinical team and the investigator will review safety data in a blinded aggregate form. In the event of concern over a potential safety signal, the GSK clinical team and the investigator may review unblinded treatment assignments for the purposes of safety review and dose selection without study interruption. If a safety signal is determined to indicate findings in subjects who received gepotidacina, the findings will be escalated for assessment by the GSK safety team and actions taken as appropriate including review of study for possible halting of further dosing.

6.5. Packaging and Labeling

The contents of the label will be in accordance with all applicable regulatory requirements.

6.6. Preparation/Handling/Storage/Accountability

No special preparation of study treatment is required.

- The investigator or designee must confirm appropriate temperature conditions have been maintained during transit for all study treatment received and any discrepancies are to be reported and resolved before use of the study treatment.

- Only subjects enrolled in the study may receive study treatment and only authorized clinic staff may supply or administer study treatment. All study treatments must be stored in a secure environmentally controlled and monitored (manual or automated) area in accordance with the labelled storage conditions with access limited to the investigator and authorized clinic staff.
- The investigator, institution, or the head of the medical institution (where applicable) is responsible for study treatment accountability, reconciliation, and record maintenance (i.e., receipt, reconciliation, and final disposition records).
- Further guidance and information for final disposition of unused study treatment are provided in the Study Reference Manual (SRM).
- Under normal conditions of handling and administration, study treatment is not expected to pose significant safety risks to clinic staff.
- A Material Safety Data Sheet or equivalent document describing occupational hazards and recommended handling precautions either will be provided to the investigator, where this is required by local laws, or is available upon request from GSK.

6.7. Compliance With Study Treatment Administration

When subjects are dosed at the clinic, they will receive study treatment directly from the investigator or designee, under medical supervision. The date and time of each dose administered in the clinic will be recorded in the source documents. The dose of study treatment and study subject identification will be confirmed at the time of dosing by a member of the clinic staff other than the person administering the study treatment. Study site personnel will examine each subject's mouth to ensure that the study treatment was ingested.

6.8. Treatment of Study Treatment Overdose

Gepotidacin (all parts) or placebo (Part 3 only) will be administered at the clinic, thus limiting the risk of overdose. In the unlikely event that an overdose with gepotidacin should occur, the investigator must notify the sponsor promptly. There is no specific antidote for overdose with a bacterial topoisomerase inhibitor such as gepotidacin. In the event of a suspected overdose, it is recommended that the appropriate supportive clinical care should be instituted, as dictated by the subject's clinical status.

GlaxoSmithKline does not recommend specific treatment for an overdose.

In the event of an overdose the investigator should:

1. Contact the medical monitor immediately.
2. Closely monitor the subject for AEs/SAEs and laboratory abnormalities until gepotidacin can no longer be detected systemically (at least 3 days for gepotidacin).

3. Obtain a plasma sample for PK analysis within 3 days from the date of the last dose of study treatment if requested by the medical monitor (determined on a case-by-case basis).
4. Document the quantity of the excess dose as well as the duration of the overdosing in the eCRF.

Decisions regarding dose interruptions or modifications will be made by the investigator in consultation with the medical monitor based on a clinical evaluation of the subject.

6.9. Treatment After the End of the Study

Subjects will not receive any additional treatment from GSK after completion of the study because only healthy volunteers are eligible for study participation.

6.10. Lifestyle and/or Dietary Restrictions

6.10.1. Meals and Dietary Restrictions

Standard meals will be provided during the study dosing period at specified times.

Subjects will refrain from consumption of red wine, Seville oranges, grapefruit, or grapefruit juice (and/or pummelos, exotic citrus fruits, or grapefruit hybrids) from 7 days prior to the first dose of study medication until after the final dose.

For Parts 1a and 2, subjects will fast from food and drink (except water) for at least 10 hours before dosing on Day 1 of each period. For the fed group of the food effect evaluation in Part 1b, study drug will be administered within 30 minutes after the completion of a moderate fat meal. For Part 3, study drug (gepotidacin or placebo) will be administered within 30 minutes after the completion of a standard Japanese meal.

Fasting requirements may be modified, relaxed, or removed based on emerging safety, tolerability, and PK data from Part 1a. If fasting requirements are removed, then Part 1b may be conducted as a single-period study with drug administered only under fed conditions. In the event that the formulation tested for Part 1b is not tolerated in the fasting state, subjects may receive the formulation with a meal after consultation with the sponsor and investigator.

6.10.2. Caffeine, Alcohol, and Tobacco

Subjects will abstain from ingesting caffeine- or xanthine-containing products (e.g., coffee, tea, cola drinks, and chocolate) for 24 hours prior to the start of dosing until collection of the final PK sample.

During each dosing session, subjects will abstain from alcohol for 24 hours prior to the start of dosing until collection of the final PK sample.

Use of tobacco products is not allowed from 3 months before Screening until after the final Follow-up visit.

6.10.3. Activity

Subjects will abstain from strenuous exercise for 48 hours prior to each blood collection for clinical laboratory tests. Subjects may participate in light recreational activities during the study (e.g., watch television, read).

6.11. Concomitant Medications and Non-Drug Therapies

6.11.1. Permitted Medications and Non-Drug Therapies

Hormonal contraceptives and/or acetaminophen, at doses of ≤ 2 grams/day are permitted for use. Other concomitant medication may be considered on a case-by-case basis by the investigator in consultation with the medical monitor.

All concomitant medication use will be documented on the concomitant medication page in the eCRF.

6.11.2. Prohibited Medications and Non-Drug Therapies

Subjects must abstain from taking prescription or non-prescription drugs (including vitamins and dietary or herbal supplements), within 7 days (or 14 days if the drug is a potential enzyme inducer) or 5 half-lives (whichever is longer) prior to the first dose of study medication until completion of the Follow-up visit, unless in the opinion of the investigator and sponsor the medication will not interfere with the study.

Since gepotidacin is known to have some prolongation of QTc, any drugs known to increase QTc interval should be avoided when treating an AE.

Due to the potential for acetylcholinesterase inhibition with gepotidacin, the following medications are prohibited:

- Succinylcholine or other depolarizing muscle relaxants
- Acetylcholinesterase inhibitors as required for myasthenia gravis including edrophonium, pyridostigmine, neostigmine, etc

7. STUDY ASSESSMENTS AND PROCEDURES

Protocol waivers or exemptions are not allowed with the exception of immediate safety concerns. Therefore, adherence to the study design requirements, including those specified in the Time and Events Table ([Table 9](#)), are essential and required for study conduct.

This section lists the procedures and parameters of each planned study assessment. The exact timing of each assessment is listed in the Time and Events Table ([Table 9](#)).

The following points must be noted:

- If assessments are scheduled for the same nominal time, THEN the assessments should occur in the following order:
 5. 12-lead ECG
 6. vital signs
 7. blood draws

Note: The timing of the assessments should allow the blood draw to occur at the exact nominal time.

- The timing and number of planned study assessments, including safety and PK assessments, may be altered during the course of the study based on newly available data (e.g., to obtain data closer to the time of peak plasma concentrations) to ensure appropriate monitoring.
- The change in timing or addition of time points for any planned study assessments must be documented in a Note to File which will be approved by the relevant GSK study team member and then archived in the study sponsor and clinic study files, but this will not constitute a protocol amendment.
- The institutional review board (IRB)/independent ethics committee (IEC) will be informed of any safety issues that require alteration of the safety monitoring scheme or amendment of the informed consent form.
- No more than 500 mL of blood will be collected over the duration of the study, including any extra assessments that may be required.

7.1. Time and Events Table

Table 9 Time and Events Table: All Parts

Procedure	Screening (up to 30 days prior to Day 1)	Day -1 ^a	Part 1a – Relative Bioavailability: Periods 1, 2, and 3 Part 1b – Food Effect: Periods 1 and 2 Part 2 – Pharmacokinetics: Periods 1 and 2 Part 3 - Pharmacokinetics - Fed State: Periods 1, 2, and 3												Follow-up (5 to 7 days post last dose)	
			Predose	0 h	0.5 h	1 h	1.5 h	2 h	2.5 h	3 h	4 h	6 h	8 h	12 h	24 h	
Admission to unit		X														
Informed consent	X															
Demographics including BMI	X															
Full physical examination including height and weight ^b	X															
Brief physical examination ^b		X														X
Medical/medication/drug/alcohol history	X															
12-lead ECG ^c	X	X	X					X						X	X	X
Vital signs ^d	X	X	X					X						X	X	X
Drug/alcohol/cotinine screen	X	X														
Serum pregnancy, FSH, and estradiol (women)	X	X														X
HIV antibody, HBsAg, and hepatitis C antibody screen	X															
Safety laboratory tests ^e	X	X														X
Study drug administration ^f				X												
Pharmacokinetic sampling			X	X	X	X	X	X	X	X	X	X	X	X	X	
Urine collection for pharmacokinetics (Parts 1a, 2, and 3 only) ^g		X						X		X	X	X	X	X	X	

Procedure	Screening (up to 30 days prior to Day 1)	Day -1 ^a	Part 1a – Relative Bioavailability: Periods 1, 2, and 3 Part 1b – Food Effect: Periods 1 and 2 Part 2 – Pharmacokinetics: Periods 1 and 2 Part 3 - Pharmacokinetics - Fed State: Periods 1, 2, and 3												Follow-up (5 to 7 days post last dose)	
			Predose	0 h	0.5 h	1 h	1.5 h	2 h	2.5 h	3 h	4 h	6 h	8 h	12 h	24 h	
Pharmacogenetic sample ^h				←=====→												
AE/SAE Review	X			←=====→												X
Concomitant medication review		X		←=====→												X
Discharge ⁱ																X
Outpatient visit	X															X

AE = adverse event, BMI = body mass index, ECG = electrocardiogram, FSH = follicle-stimulating hormone, h = hour, HBsAg = hepatitis B surface antigen, HIV = human immunodeficiency virus, SAE = serious adverse event.

- ^a The Day -1 visit occurs in Period 1 only. Periods 2 (all parts) and 3 (Parts 1a and 3 only) begin on Day 1.
- ^b A complete physical examination will include at a minimum, assessment of the cardiovascular, respiratory, gastrointestinal, and neurological systems. Height and weight will also be measured and recorded. A brief physical examination will include, at a minimum, assessments of the skin, lungs, cardiovascular system, and abdomen (liver and spleen).
- ^c Triplicate 12-lead ECGs will be measured in semi-supine position after 5 minutes rest and obtained at least 5 minutes apart on Day -1. Single 12-lead ECGs will be measured in semi-supine position after 5 minutes rest at all other time points during the study
- ^d Single vital signs will be measured in semi-supine position after 5 minutes rest and will include systolic and diastolic blood pressure, and heart rate. Body temperature and respiratory rate will be collected at Screening only.
- ^e Safety laboratory tests include serum chemistry, hematology, and urinalysis.
- ^f Subjects will fast from food and drink (except water) for at least 10 hours before study drug administration on Day 1 of each period. For the fed group of the food effect evaluation in Part 1b, study drug will be administered within 30 minutes after the completion of a moderate fat meal. For Part 3, study drug will be administered within 30 minutes after completion of a standard Japanese meal.
- ^g Urine collection intervals (Parts 1a, 2, and 3 only) for subjects include 0 (predose), 0 to 2 hours, 2 to 4 hours, 4 to 6 hours, 6 to 8 hours, 8 to 12 hours, 12 to 24 hours, 24 to 36 hours, and 36 to 48 hours.
- ^h For subjects who consent only: collect 1 pharmacogenetic sample after the start of dosing (preferably Day 1). Informed consent for optional pharmacogenetics research must be obtained before collecting a sample.
- ⁱ For Parts 1a and 3, subjects will be discharged from the clinical research unit on Day 3 of Period 3. For Parts 1b and 2, subjects will be discharged on Day 3 of Period 2.

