Part 3 is a 3-period, randomized, double-blind, placebo-controlled, fixed-sequence study and will evaluate the safety, tolerability, and pharmacokinetics of single ascending doses of 1500 mg, 2250 mg, and 3000 mg gepotidacin tablet formulation selected from Part 1a or placebo in a cohort of Japanese subjects in the fed state. See the study schematic in [Table 4](#) for more details.

Table 4 Part 3 Pharmacokinetic Study Design Schematic - Fed State

Treatment	Fixed-sequence					Follow-up
RC, HSWG, or placebo tablet - fed ^a	Period 1	Wash-out At least 3 days	Period 2	Wash-out At least 3 days	Period 3	5 to 7 days after final dose
Sequence 7	E or I		G or I		H or I	

HSWG = high shear wet granulation; RC = related compound.

^a 1500 mg single dose given as 2 × 750-mg RC or HSWG (Treatment E) tablets – fed; 2250 mg single dose given as 3 × 750-mg RC or HSWG (Treatment G) tablets – fed; 3000 mg single dose given as 4 × 750-mg RC or HSWG (Treatment H) tablets – fed; or placebo (Treatment I) tablets – fed

Subjects will be stratified by gender in a 1:1 ratio and randomly assigned (10 active: 2 placebo) to receive gepotidacin or placebo. For each period, a sentinel group of up to 4 subjects will be dosed with study drug and evaluated for safety and tolerability prior to dosing the remaining subjects. The adverse event profiles will be reviewed before escalating to the next dose. Subjects will participate in 3 treatment periods and blood and urine samples will be collected for PK analysis of gepotidacin concentrations according to the Time and Events Table ([Table 9](#)). Blood and urine samples will be collected up to approximately 48 hours after dosing.

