On Day 1 (Period 1), subjects will receive a single 1500-mg (2×750 mg) dose of gepotidacin tablet (RC or HSWG) selected from Part 1a. On Day 1 of Period 2, subjects will receive a single 3000-mg (4×750 mg) dose of gepotidacin tablet (RC or HSWG) selected from Part 1a. There will be a washout period of at least 3 days between doses.

Subjects will remain in the clinical research unit from Day -1 until Day 3 of Period 2 after all scheduled PK and safety assessments have been completed, and will return to the clinic for a Follow-up visit approximately 5 to 7 days after the final dose of study drug. The duration of the study (from Screening to the Follow-up visit) will be approximately 41 days.

Part 3: Pharmacokinetics in Japanese Subjects - Fed State

- Treatment E: Gepotidacin 1500 mg (2 × 750 mg) RC or HSWG tablets - fed
- Treatment G: Gepotidacin 2250 mg (3 × 750 mg) RC or HSWG tablets - fed
- Treatment H: Gepotidacin 3000 mg (4 × 750 mg) RC or HSWG tablets - fed
- Treatment I: Placebo tablets - fed

On Day 1 (Period 1), subjects will be stratified by gender in a 1:1 ratio and randomly assigned (10 active: 2 placebo) to receive gepotidacin tablet (RC or HSWG) selected from Part 1a in an ascending manner (Treatments E, G, and H) on Day 1 of Periods 1, 2, and 3, respectively, or placebo. For each period, a sentinel group of up to 4 subjects will be dosed with study drug and evaluated for safety and tolerability prior to dosing the remaining subjects. There will be a washout period of at least 3 days between doses. The adverse event profiles will be reviewed before escalating to the next dose. Subjects will remain in the clinical research unit from Day -1 until Day 3 of Period 3 after all scheduled PK and safety assessments have been completed, and will return to the clinic for a Follow-up visit approximately 5 to 7 days after the final dose of study drug. The duration of the study (from Screening to the Follow-up visit) will be approximately 44 days.

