5.4.1. Liver Chemistry Stopping Criteria

Liver chemistry stopping and increased monitoring criteria have been designed to assure subject safety and evaluate liver event etiology in alignment with the FDA guidance, “Drug-Induced Liver Injury: Premarketing Clinical Evaluation,” [DHHS, 2009].

Study treatment will be stopped if the following liver chemistry stopping criterion is met:

- ALT $\geq 3 \times$ ULN

For details of the required assessments if a subject meets the above criteria, refer to [Appendix 2](#), Liver Chemistry Stopping Criteria.

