5.4.2. QTc Stopping Criteria

- The same QT correction formula must be used for each individual subject to determine eligibility for and discontinuation from the study. This formula may not be changed or substituted once the subject has been enrolled.
 - For example, if a subject is eligible for the protocol based on the QTcF, then the QTcF must be used for discontinuation of this individual subject as well.
 - Once the QT correction formula has been chosen for a subject’s eligibility, the *same formula* must continue to be used for that subject *for all QTc data being collected for data analysis*. Safety ECGs and other non-protocol specified ECGs are an exception.
 - The QTc should be based on single or averaged QTc values of triplicate ECGs obtained over a brief (e.g., 5 to 10 minute) recording period.

A subject who meets either bulleted criterion below will be withdrawn from the study:

- QTc > 500 msec
- Increase from baseline of QTc > 60 msec

For subjects with underlying bundle branch block, the following discontinuation criteria will be used instead:

Baseline QTc With Bundle Branch Block	Discontinuation QTc With Bundle Branch Block
<450 msec	>500 msec
450 to 480 msec	≥ 530 msec

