10.3.2. Baseline Definition & Derivations

10.3.2.1. Baseline Definitions

For all endpoints (expect as noted in the table) the baseline value will be the latest pre-dose assessment and are applicable to each period.

Table 9 Baseline Definitions

Parameter	Study Assessments Considered As Baseline			Baseline Used in Data Display
	Screening	Day -1	Day 1 (Pre-Dose)	
Safety				
Hematology	X	X		Day -1
Clinical Chemistry	X	X		Day -1
12 Lead ECG	X	X	X	Day 1 (Pre-dose)
Vital Signs	X	X	X	Day 1 (Pre-dose)

NOTES :

- Unless otherwise stated, the mean of replicate assessments at any given time point will be used as the value for that time point.

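### Part 3 schedules no laboratory panel on Day 1 pre-dose of Periods 2 and 3, and no escalation text requires an ALT result before the 2250 mg or 3000 mg dose

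*Protocol*

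**What the plan says.** **Dosing and stay.** In Part 3 the active subjects receive 1500, 2250 and 3000 mg in Periods 1, 2 and 3. Protocol Section 4.2 says: "There will be a washout period of at least 3 days between doses". Section 4.1 adds: "Blood and urine samples will be collected up to approximately 48 hours after dosing". Subjects remain in the unit until Day 3 of Period 3.

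**Laboratory schedule.** The Table 9 row "Safety laboratory tests" covers serum chemistry (which includes ALT, per Table 10), hematology and urinalysis. It is marked at Screening, at Day -1 and at one late time point. Footnote a limits Day -1: "The Day -1 visit occurs in Period 1 only. Periods 2 (all parts) and 3 (Parts 1a and 3 only) begin on Day 1".

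**Baseline.** SAP Section 10.3.2.1 states: "For all endpoints (expect as noted in the table) the baseline value will be the latest pre-dose assessment and are applicable to each period". Its table marks hematology and chemistry at Screening and Day -1 only. ECG and vital signs also have a Day 1 pre-dose mark.

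**Stopping rules.** Section 5.4.1 reads: "Study treatment will be stopped if the following liver chemistry stopping criterion is met". The criterion is ALT at or above 3 times the upper limit of normal. Section 5.4.2 on QTc reads: "A subject who meets either bulleted criterion below will be withdrawn from the study".

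**Escalation.** Sections 4.1 and 4.2 say: "The adverse event profiles will be reviewed before escalating to the next dose". Section 6.4 has the sponsor's team and the investigator look at safety data in blinded, aggregate form. Section 7.3 allows laboratory time points to be added but does not require it.

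**The concern.** Each Part 3 period is a single dose. A rule that stops treatment on an ALT result can therefore act in only one way: by withholding the 2250 mg dose or the 3000 mg dose. For that, an ALT has to be drawn and read between doses.

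The QTc rule has a scheduled pre-dose reading in every period. The ALT rule has none in Periods 2 and 3. Whether it has a later post-dose sample from the preceding period depends on where the one late laboratory mark in Table 9 falls. If that mark is Follow-up, a subject with a symptomless ALT rise after 1500 mg would go on to 2250 mg and 3000 mg with no scheduled test able to trigger Section 5.4.1. An aggregate safety review cannot include a result that was never collected.

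**Working it through.** No power or sample-size figure is involved. The check is of the calendar, the schedule and the escalation wording.

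1. **Calendar at the minimum washout.** Doses fall on Days 1, 4 and 7; the 48 h points on Days 3, 6 and 9; Follow-up (5 to 7 days after the last dose) on Days 12 to 14. With 30 days of screening, 30 + 14 = 44 days, which matches the duration stated in Section 4.2.

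2. **Pre-dose panels.** Footnote a removes Day -1 from Periods 2 and 3, and neither Table 9 nor the SAP baseline table has a laboratory mark at Day 1 pre-dose. Later periods with a scheduled pre-dose panel: 0 of 2. This holds wherever the late mark belongs.

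3. **Escalation wording.** Sections 4.1 and 4.2 name adverse event profiles, and Section 6.4 names safety data. The second is broader: laboratory tests are among the safety endpoints in Section 3, and a clinically significant laboratory abnormality counts as an adverse event under Section 12.5.1. A result that exists would therefore be seen. Nothing requires that one exist.

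4. **Where the late mark falls.** Cells below are counted after the row label.
   - *For Follow-up.* In the first block of Table 9, PK sampling occupies cells 3 to 15. The laboratory row has cells 1, 2 and 16, the same as the pregnancy test. ECG has separate marks in 15 and 16. The SAP copy in Appendix 1 also puts the late laboratory mark one cell beyond the last PK mark. The superseded original protocol, used here only as a key to the columns, has laboratory marks in both 15 and 16. Amendment 1 and the current table keep only 16.
   - *Against certainty.* The 36 h and 48 h headings are lost from Table 9. In its continuation block, Discharge (a Day 3 event) and the outpatient Follow-up visit both sit in cell 16. Some marks are plainly displaced: PK sampling appears at 0 h, and predose urine under Day -1. Neither amendment summary mentions dropping a panel.
   - *Result.* Follow-up is the more likely position, but it is not proven.

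5. **Size under each reading.** There are 10 × 3 = 30 planned active subject-doses, of which 10 × 2 = 20 follow an earlier dose.

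| Late mark is | Escalation steps with a scheduled ALT since the previous dose | Active doses given after an earlier dose without one |
|---|---|---|
| Follow-up only | 0 of 2 | 20 of 30 |
| 48 h of each period | 2 of 2 | 0 of 30 |

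On the Follow-up reading the first post-dose ALT comes on Days 12 to 14, which is 11 to 13 days after the first dose. On the 48 h reading each sample precedes the next dose by at least 72 − 48 = 24 h.

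6. **Blood volume with two added panels.** PK: 14 draws (predose, eleven times from 0.5 to 24 h, then 36 and 48 h) × 3 mL × 3 periods = 126 mL. The genetic sample is 6 mL. Panel volume is not given, so 5, 10 and 20 mL are assumed. Five panels (Screening, Day -1, Follow-up and two new) take 25, 50 or 100 mL. Totals: 126 + 6 + 25 = 157 mL, 182 mL and 232 mL, excluding serology and pregnancy tests. The Section 7 limit is 500 mL.

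**The case against.** The strongest reply is that a damaged table is not a defect in the plan. The quoted footnote removes only the Day -1 visit and says nothing about a 48 h sample, and the SAP table defines baselines rather than the schedule. A 48 h panel would serve escalation fully without any pre-dose panel. The original protocol had two late laboratory marks, and no amendment summary announces the loss of one. All of this stands, and it is why the between-dose gap is stated conditionally.

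The reply continues that Section 5.4.1 already stops treatment, Section 6.4 already reviews safety data, and Section 7.3 already allows extra tests. This stands in part. Those provisions deal with a result once it is in hand; none requires that an ALT be drawn and read before the next dose.

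Finally, the risk case is thin. Section 4.6.1 lists gastrointestinal, cardiovascular, acetylcholinesterase and rash risks, with no hepatic signal. Section 4.5 cites prior single doses to 3000 mg and repeat dosing to 2300 mg twice daily. A pre-dose ECG without a pre-dose ALT is understandable for a drug with a known QT effect. This stands and keeps the priority low, although SAP Section 10.4.3 does list liver events among the adverse events of special interest.

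A reader might infer two stronger things: that no ALT at all is scheduled between ascending doses, and that escalation ignores laboratory data. The documents support neither. The first depends on a column position that cannot be read with certainty, and the second is contradicted by Section 6.4.

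**Conclusion.** The point holds as a minor, inexpensive improvement. Two facts are firm: no laboratory panel is scheduled on Day 1 pre-dose of Part 3 Periods 2 and 3, and no escalation text makes an ALT result a condition of the next dose.

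That the ALT rule has no scheduled result to act on before 2250 mg and 3000 mg is likely but conditional on the late mark being Follow-up. The figures of 0 of 2 escalation steps and 20 of 30 active doses apply only then. If the PDF shows a 48 h mark in each period, the sampling is adequate and only the review wording is missing. The sponsor can settle this by looking at the table.

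**What to change.** First, check the laboratory row of Table 9 in the PDF. If 48 h is not marked, mark safety laboratory tests at the existing 48 h draw of Part 3 Periods 1 and 2, in Table 9 and in SAP Appendix 1, and keep Follow-up. A 48 h panel in Period 3 is not needed for this purpose, since no dose follows it.

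On either reading, add to Sections 4.2 and 6.4: *Each subject's 48-hour ALT result will be reviewed against Section 5.4.1 before that subject's next dose.*

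The cost is two extra tubes per subject at an inpatient draw that already takes place, about 10 to 40 mL in all on the assumed panel volumes and well within the blood limit. The practical constraint is turnaround. At the minimum washout the laboratory has about 24 h to return the ALT; otherwise the next dose waits. The washout is stated as a minimum, so a short delay is within the protocol.
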